9.5 Response criteria for liver metastases

The response of liver metastases will be evaluated by MRI or CT scans using the criteria

Complete Response (CR)	Disappearance of all target and non-target liver lesions
Partial Response (PR)	> 30% decrease in the sum of the longest diameters ("sum LD") relative to baseline sum LD with at least stable non-target liver lesions
Stable Disease (SD)	Absence of change which would qualify as response or progression
Progression (PD)	≥ 20% increase in the sum LD in target liver lesions or unequivocal progression of non-target liver lesions in the treated lobe(s) Appearance of one or more new liver lesions ≥10 mm in the treated lobe(s)

adapted from the international criteria proposed by RECIST 1.1. However, since there can be post embolization changes in liver tumors that can sometimes be read as lesion enlargement, post treatment changes will be considered when lesions are measured.

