4.0 SUBJECT SELECTION AND WITHDRAWAL

4.1 Inclusion Criteria

- Histologically confirmed metastatic uveal melanoma in the liver. Patients must have at least one measurable liver metastasis that is ≥ 10 mm in longest diameter by CT scan or MRI.
- 2. The total volume of the tumors must be less than 50% of the liver volume.
- 3. Willingness and ability to give informed consent.
- 4. Agreement to access archival tissue or agreement for tumor biopsy prior to treatment
- 5. ECOG performance status of 0, or 1
- 6. Adequate renal and bone marrow functions: serum creatinine ≤ 2.0 mg/dl, granulocyte count ≥ 1000/mm3, and platelet count ≥ 100,000/mm3.
- 7. Adequate liver function: bilirubin ≤ 2.0 mg/ml, albumin ≥ 3.0 g/dl, PT/PTT less than 1.5 times normal, AST and ALT less than 3x ULN and alkaline phosphatase less than 1.5 times ULN (grade 1).
- 8. Age \geq 18 years of age.
- 9. Women must not be pregnant or breast-feeding. See section 4.2.1
- 10. Women of child-bearing potential must use at least two other accepted and effective methods of contraception and/or to abstain from sexual intercourse for at least 23 weeks after the last dose of nivolumab and/or ipilimumab and sexually active males must use at least two other accepted and effective methods of contraception and/or to abstain from sexual intercourse for at least 31 weeks after the last dose of nivolumab and/or ipilimumab. See section 4.2.1

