Patients who experience progressive disease by RECIST criteria without clinical deterioration may continue on protocol therapy until their next scheduled scan if the investigator feels the patient may be having clinical benefit and may experience a delayed or atypical response. Only patients who have no progression of symptoms of cancer, no decline in performance status, and no progression of tumor at a critical anatomic site (e.g., cord compression) will be eligible for the treatment beyond progression. If the next scheduled scan shows a further increase in tumor measurements (>10% RECIST target lesions or unequivocal progression of non-target lesions) from the scan that first suggested progression, patient will be deemed to have true progression and patient will be removed from study. It the next scheduled scan does not show further progression, patient will remain on study treatment.

For patients who achieved PR, CR, or SD in the liver metastases after embolization, tumor measurements should be continued after every 2 IEMBO treatments for up to 2 years after initiation of protocol therapy or until PD is confirmed.

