7.2.1 Analysis Population

The evaluable population includes all subjects enrolled who receive at least four combination treatments (IPI + NIVO + IEMBO at initial every 3 week intervals or NIVO + IEMBO if IPI dropped due to toxicity and IEMBO alone if NIVO dropped due to toxicity) and complete assessment after four treatments.

The As-treated population includes all subjects who receive any treatment and will be used to evaluate baseline characteristics as well as all secondary endpoints for safety and efficacy as the collected data allows.

7.2.2 Primary Endpoint:

The primary endpoint is the best hepatic response (CR + PR + SD) by response criteria (RECIST 1.1) after four combination treatments. The estimate of the hepatic metastasis stabilization rate will be presented with corresponding 95% confidence intervals. The method of Atkinson and Brown will be used to adjust for the two-stage design.

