9.4 Evaluation of overall response in the liver metastases

Clinical response in the liver metastases will be evaluated using CT scans or MRI of the abdomen initially following four combination treatments and then after every two IEMBO treatments. The same modality must be used for serial measurements of target lesions. The sum of the longest diameter (LD) of up to 6 target liver lesions will be used to determine response. The investigators must identify target indicator lesions and measure them prior to the first embolization as baseline. The investigators will then measure the same target lesions after every two IEMBO treatments.

The sum of the baseline LDs will be compared to the sum of LDs after every two IEMBO treatments following the scans after the first four treatments. New lesions will be defined as lesions that appear in the treated lobe(s) of the liver after the last evaluation and should be \geq 10 mm in longest diameter. Development of new lesion(s) in an untreated lobe (area) of the liver **will not** be considered as "Progressive Disease" for evaluation of liver response. These lesions will be treated in the subsequent embolization procedures and

they will be included in the evaluation for response after completion of two additional embolizations.

Target Liver Lesions	Non-Target Liver Lesions	New Liver Lesions in the treated lobes	Overall Liver Response
CR	CR	No	CR
CR	SD	No	PR
PR	Non-PD	No	PR
SD	Non-PD	No	SD
PD	Any	Yes or No	PD
Any	PD	Yes or No	PD
Any	Any	Yes	PD

To be assigned a status of CR or PR, changes in tumor measurements must be confirmed by the follow-up assessment using the same imaging test at a minimum interval of 4 weeks. The patients who have a CR or PR without confirmatory assessment will be categorized as SD. In the case of SD, follow-up measurements must have met the SD criteria at least once at a minimum interval of 4 weeks. The patients who have a SD without confirmatory assessment will be categorized as PD.

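### Target-lesion PD has no minimum change in millimetres, so for small baseline sums a 2–3 mm reading difference can turn stable disease into a primary failure

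*Combined protocol and SAP*

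**What the plan says.** Section 9.5 sets the target-lesion threshold at "≥ 20% increase in the sum LD in target liver lesions", with no absolute minimum. The criteria are described as "adapted from the international criteria proposed by RECIST 1.1", so the table in 9.5 is the operative text. No other section supplies a minimum: the 10 mm limit in 9.4 and 9.5 applies to new lesions only.

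Eligibility (4.1, no. 1) asks for "at least one measurable liver metastasis that is ≥ 10 mm in longest diameter by CT scan or MRI", and 9.3 applies the same size limit to each target lesion. Section 9.4 adds: "The sum of the longest diameter (LD) of up to 6 target liver lesions will be used to determine response". Change is measured from the baseline sum, by the investigators.

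Section 7.2.2 states: "The primary endpoint is the best hepatic response (CR + PR + SD) by response criteria (RECIST 1.1) after four combination treatments". Under 9.4, SD needs a confirming assessment at an interval of at least 4 weeks, and unconfirmed SD is recoded to PD.

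Three other provisions bear on the point. Section 6.1.5, for patients treated beyond progression, takes a further increase as true progression on another bare percentage: ">10% RECIST target lesions or unequivocal progression of non-target lesions". Section 9.6 dates PFS to confirmation of progression without defining confirmation. Section 9.5 also tells readers that "post treatment changes will be considered when lesions are measured".

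**The concern.** Success is CR, PR or SD, so the line between SD and PD decides the primary result. A rule stated only as a percentage asks for very little growth when the baseline sum is small. Section 9.2 itself acknowledges that radiological assessment after embolization is hard. If reading error alone can cross the line, some unchanged patients are counted as failures, the measured stabilization rate drops, and a design with little power to spare loses some of it.

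**Working it through.** **1. The plan's own figures.** Sections 7.1 and 7.2 give 13 patients in stage 1 (stop at 8 or fewer successes) and 35 in total (ineffective at 25 or fewer). With X ~ Bin(13, p) and Y ~ Bin(22, p), the probability of early stopping is P(X ≤ 8), and the probability of rejecting the null is the sum over x = 9 to 13 of P(X = x) · P(Y ≥ 26 − x).

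- p = 0.60: early stopping 0.647, rejection 0.0499.
- p = 0.80: rejection 0.808, so type II error is 0.192.

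These reproduce the stated 0.65, 5% and 19%.

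**2. Millimetres needed for PD.** The threshold is 0.20 × baseline sum: 2 mm at 10, 3 mm at 15, 4 mm at 20, 5 mm at 25, 6 mm at 30 and 12 mm at 60. A minimum of A mm changes the call only when 0.20 × sum < A, that is, when the sum is below 5A. For A = 5 mm that means sums under 25 mm.

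**3. Chance of false PD at one scan.** Assumptions, not in the documents: independent reading errors with SD s = 1.0–1.5 mm per diameter, and true sizes spread evenly around the baseline reading b. For one unchanged lesion the difference of two readings has SD s√2, so

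P(false PD) = 1 − Φ(0.2b / (s√2)).

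At b = 10 and s = 1.0 this is 1 − Φ(2/1.414) = 7.9%. At s = 1.5 it is 1 − Φ(2/2.121) = 17.3%.

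| Baseline reading | s = 1.0 | s = 1.5 |
|---|---|---|
| 10 mm | 7.9% | 17.3% |
| 15 mm | 1.7% | 7.9% |
| 20 mm | 0.2% | 3.0% |
| 25 mm | 0.02% | 0.9% |
| average over 10–15 mm | 4.2% | 12.1% |
| average over 10–25 mm | 1.7% | 6.3% |

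With a 5 mm minimum, every single-lesion row becomes 1 − Φ(5/(s√2)) = 0.02% (s = 1.0) or 0.9% (s = 1.5).

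With k lesions the SD of the difference is s√(2k). For two 10 mm lesions (sum 20 mm), false PD is 2.3–9.1% under the percentage alone and 0.6–4.8% with the 5 mm minimum. For three (sum 30 mm) it is 0.7–5.1% either way, because the minimum no longer binds. The reduction to under 1% is thus a single-lesion result.

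**4. Effect on power.** Let f = share of patients with small sums × false-PD rate in them. The measured rate is 0.80 × (1 − f). The share is assumed to be 10–30%.

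| Share × rate | f | Measured rate | Power |
|---|---|---|---|
| none | 0 | 80.0% | 80.8% |
| 10% × 2% | 0.2% | 79.8% | 80.2% |
| 30% × 2%, or 10% × 6% | 0.6% | 79.5% | 78.9% |
| 30% × 6% | 1.8% | 78.6% | 74.9% |
| 30% × 8% | 2.4% | 78.1% | 72.7% |

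The range of roughly 73–80% thus uses rates of 2–8% in the affected group. Pairing the 30% share with 12% gives f = 3.6% and power of 68%. That would need nearly a third of patients to have a single lesion of 10–15 mm and the larger reading error as well.

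Under the null, the same misreading lowers type I error: 0.043 at f = 1% and 0.037 at f = 2%.

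**5. The second-scan rule.** PD followed by a further increase of more than 10% needs a reading above 1.20 × 1.10 = 1.32 times baseline, or more than 13.2 mm from 10 mm. Simulated under the assumptions of step 3, an unchanged lesion read at 10–15 mm meets both conditions in about 0.5% of cases or fewer.

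**The case against.** The strongest case against is that the size of the effect is unknown. The documents give neither a reading error nor the distribution of baseline sums. Targets are chosen by size and up to six are summed, so a lone 10 mm target is the extreme case. The false-PD rate also depends on conditioning. For a lesion whose true size is exactly 10 mm, keeping only baselines read at 10 mm or more, one-scan false PD is 0.5–2.6%, because such lesions tend to be read high at entry. Error also runs both ways, since true growth can be read as SD. All of this stands and limits the magnitude. In the other direction, a stable patient needs SD at more than one reading under 9.4, and step 3 counts one scan only.

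Safeguards exist. Section 9.2 obtains both CT and MRI and keeps to one modality for measurement, and 9.5 allows for post-treatment change. They help, but the allowance in 9.5 is unquantified judgement by investigators in an open-label trial.

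The null of 60% may rest on a percent-only rule. A higher bar for PD in this trial alone would then favour rejection. This does not defeat the change, but it means that both results must be shown.

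A reader might infer more than the documents support:

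- Power as low as 62%. This needs about 17% misreading in 30% of patients, as if all of them had a single lesion read at exactly 10 mm with the larger error.
- Any 2 mm difference is a PFS event. Section 9.6 requires confirmation, although it leaves the term undefined.
- PD and the further 10% increase both lie within reading error. Each step is small, but step 5 shows that the two together are rare.
- The error builds up with each scan. The primary endpoint is best response, so later PD does not undo a confirmed SD.

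**Conclusion.** The gap in the text is certain: 9.5 has no absolute minimum, one 10 mm lesion suffices for entry, and the SD/PD line is the primary success line. Its size is conditional on two assumptions, a reading SD of 1.0–1.5 mm and a 10–30% share of patients with sums under 25 mm. On these, the cost is between under one and about eight percentage points of power. The net loss is smaller if the 60% historical rate carries the same reading error. The direction is conservative. The stated sample size and error rates are correct for the rates they assume. This is a worthwhile, inexpensive improvement and does not put the trial's conclusion in doubt.

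**What to change.** In 9.5, define target-lesion PD as a 20% increase in sum LD together with a prespecified minimum absolute increase. The 5 mm used here is an illustration; the sponsor should check the figure against the RECIST 1.1 reference cited in 9.2. Fix it before outcomes are reviewed, because it moves the success boundary. Report the primary result under the percent-only rule as well, and state which rule produced the 60% null.

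Sections 6.1.5 (further increase of more than 10%) and 9.6 (confirmation of progression) must be reconciled with the revised definition.

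The cost is one line in 9.5, a second tabulation and the reconciliation. The downside is that true growth below the minimum in small lesions is called later, and the success rate may come out slightly higher than under a percent-only historical rule.

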9.6 Progression Free Survival

Progression Free Survival (PFS) is measured from the start of the treatment to confirmation of progression of disease by either imaging tests or physical examination. Date and sites of progression will be recorded. Progression free interval for hepatic metastases and progression free interval for extra-hepatic metastasis will be measured in aggregate and separately.

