3.3 Secondary Study Endpoints

- 1. All toxicities using the NCI CTCAE Version 4.0.
- 2. Progression Free Survival (hepatic and systemic PFS)
- 3. Overall survival

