4.3.2 Data Collection and Follow-up for Withdrawn Subjects

Subjects who are withdrawn from the study and permanently discontinued from receiving on study treatment will be followed for safety, including the collection of any protocol-specified blood specimens, unless consent if withdrawn or the subject is lost to follow up or enrolled in another clinical trial. All subjects will be followed for survival. Any subjects who are unable to return to the site for visits will be offered to follow up by phone every three months for at least one year.

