6.1.7 Follow-up after study completion

All patients, including patients who discontinue protocol therapy because of toxicity or progressive disease must be followed every three months up to a minimum of 1 year to determine clinical status and to document time to progression and duration of survival. Telephone contact is allowed for this purpose.

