7.2.3 Secondary and Exploratory (Correlative) Endpoints

- 1. All toxicities using the NCI CTCAE Version4.0.
- 2. PFS (hepatic and systemic PFS)
- 3. Overall survival
- 4. Systemic and local immune/inflammatory response correlatives
 - a. Degree and classification of tumor-infiltrating cells
 - b. Presence and changes in PD-L1 expression in tumor and tumor-infiltrating cells
 - c. Changes in immune tumor microenvironment (immune gene signature)
 - d. Tumor mutational burden prior to treatment
 - e. Changes in TCR repertoire analysis (ImmunoSeq)
 - f. Changes in cytokine levels (multiplex cytokine measurements)
 - g. Changes in PBMC cell populations, including T cells and MDS.

The PFS and OS will be estimated using the Kaplan-Meier method. The toxicity rates will be estimated with corresponding 95% confidence intervals. Correlative endpoints including repeated measures of cytokine and molecular marker levels in tissue or serum will be analyzed using appropriate linear mixed effects models.

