9.7 Overall survival

Overall survival (OS) is measured from the start of the treatment to death of patients. Date and cause of death will be recorded. The cause of death will be categorized as either cancer-related or cancer-unrelated.

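### PFS in section 9.6 ends only at confirmed progression; no section counts death as an event, so as written the Kaplan-Meier estimate is time to progression reported as PFS

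*Combined protocol and SAP*

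**What the plan says.** All references are to the combined protocol and SAP.

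- **9.6** gives the only definition of PFS: it "is measured from the start of the treatment to confirmation of progression of disease by either imaging tests or physical examination". It adds that progression-free intervals for hepatic and extra-hepatic disease are measured both together and separately. Death does not appear.
- **3.3** lists hepatic and systemic PFS as a secondary endpoint without defining the event. **7.2.3** repeats the name and gives the estimator: "The PFS and OS will be estimated using the Kaplan-Meier method". There is no event list, censoring rule or competing-risk method.
- **9.7** is where death is an endpoint: "Overall survival (OS) is measured from the start of the treatment to death of patients".
- **6.1.7** sets out follow-up "to determine clinical status and to document time to progression and duration of survival", naming progression and survival as two separate items.
- **7.2.1** assigns the secondary endpoints to the as-treated population, "all subjects who receive any treatment and will be used to evaluate baseline characteristics as well as all secondary endpoints for safety and efficacy", qualified by what the collected data permit. **9.1** excludes patients who could not receive immunoembolization for technical reasons from the evaluation of clinical response, which it describes as including survival.

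**The concern.** PFS is normally understood to end at progression or death, whichever comes first. Section 9.6 names progression alone. A patient who dies before progression is confirmed, for instance before the first scan or between a scan suggesting progression and the one confirming it, is in the analysis without a defined event. Kaplan-Meier then has nothing to do with that patient but stop counting follow-up.

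This is a single-arm trial, so its PFS can be interpreted only against results from elsewhere. An estimate that leaves deaths out is not comparable with PFS that includes them, and the usual effect is to make the regimen look better. An analyst who follows 9.6 and one who follows the name of the endpoint would also report different curves from the same data.

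**Working it through.** **1. Is there a plan figure to reproduce?** Not for PFS: the documents give no PFS median, rate or event count. The only design figures belong to the two-stage primary endpoint (13 then 35 patients; stop at 8 or fewer, reject the null at 26 or more). Exact binomial calculation gives early stopping 0.647 and type I error 0.0499 at a 60% rate, and power 0.808 at 80%. The plan states 0.65, 5% and 80% (a type II error of 19% in 7.2), so these agree to rounding. PFS enters none of them.

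**2. What the text does with a death.** Take a treated patient who dies at week 9 with no confirmed progression. For OS (9.7) this is an event. For PFS (9.6) no event has occurred. Neither 3.3, 6.1.7 nor 7.2.3 supplies one.

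**3. Direction.** Suppose the patient is censored at the date of death. The risk sets for the two curves are then identical at every time. At each progression time without a death, both curves are multiplied by the same factor. At a time with d deaths among n at risk, true PFS is multiplied by (1 - d/n) and the censored curve by 1. With progressions and deaths on the same date, the censored factor is still the larger. So the censored curve is at or above true PFS throughout.

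This depends on the censoring date. Suppose deaths were censored at the last scan instead. Patient A is scanned at week 12 and dies at week 19; patient B progresses on physical examination at week 13; n = 35.

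| Weeks | True PFS | Censored curve |
|---|---|---|
| 13 to 19 | 34/35 = 0.971 | 33/34 = 0.971 (0.9706 against 0.9714) |
| after 19 | 33/35 = 0.943 | 33/34 = 0.971 |

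The curve is briefly and very slightly lower, then higher.

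**4. Size, constant hazards (assumed).** Let m be the true PFS median and f the share of first events that are deaths without confirmed progression. The PFS hazard is ln2/m. With deaths censored, the hazard is (1-f)·ln2/m, so the median is m/(1-f), and the event-free proportion at the true median is 0.5^(1-f) instead of 0.5.

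| f (assumed) | Median multiplied by | Event-free at the true median |
|---|---|---|
| 0 | 1.00 | 50.0% |
| 2% | 1.02 | 50.7% |
| 5% | 1.05 | 51.8% |
| 10% | 1.11 | 53.6% |
| 20% | 1.25 | 57.4% |

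**5. Effect of scan timing.** Simulation with scans at weeks 6, 12 and then every 8, an assumed true median of 24 weeks, exact death dates, and progression dated at the next scan. The large-sample median is 28 weeks whether deaths are counted or censored for f up to about 15%, and 28 against 36 weeks at f = 20%. The curve moves even when the median does not: at week 28 it is 44.5% with deaths counted, and 45.2%, 46.2%, 47.9% and 51.7% with deaths censored, at f = 2%, 5%, 10% and 20%. In simulated 35-patient trials the median rose in 19%, 36% and 66% of trials at f = 5%, 10% and 20%, and fell in none.

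**The case against.** **The plan is silent rather than wrong.** It never orders that deaths be censored, and an analyst might count them because the endpoint is called PFS. The first part stands: a reader might infer that the plan prescribes censoring, and it does not. But 9.6 states a rule, and under that rule a death is not an event. Only the name argues otherwise.

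**The direction is certain.** This is tempting and too strong. It is assured only for censoring at the death date, which the plan does not specify. Step 3 shows a small local exception under another date.

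**Every treated patient is affected.** The documents do not support that breadth. Section 7.2.1 limits the as-treated analysis to what the data allow, and 9.1 removes patients who did not receive immunoembolization for technical reasons. The point concerns patients who are in the PFS analysis and die without confirmed progression.

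**Section 9.4 already catches early failures by turning unconfirmed stable disease into progression.** That rule sets a liver response category. It supplies no progression date, does not cover extra-hepatic disease and does not amend 9.6.

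**The effect may be small.** This is fair. Progression can be recorded on examination alone (9.6) and is still followed every three months after treatment (6.1.7), so deaths without it may be few. With 35 patients and no deaths at all, the simulated median ranges from 20 to 44 weeks in 95% of trials, wider than an 8-week step.

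**The scan-grid figures are not what the plan would produce.** Also fair. They date progression at the first scan, whereas 9.6 runs to confirmation, which under 6.1.5 may be the following scan. The grid is idealized too: immunoembolization intervals may stretch to 6 weeks (5.3.3) and treatment may be postponed by up to 10 weeks (6.3.3).

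**Conclusion.** The point holds as a defect in the definition of a secondary endpoint. Read literally, 9.6 with 7.2.3 produces time to progression labelled as PFS, and nothing elsewhere repairs it. With deaths censored at the death date, the reported curve equals or exceeds true PFS; under other censoring dates small local exceptions are possible.

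The size cannot be derived from the documents because f is not given. Under constant hazards the median is inflated by 2% to 25% for f between 2% and 20%. With f = 0, or if the analyst counts deaths anyway, there is no effect. The scan-grid results are illustrations of how the median can stay still while the curve shifts, and should not be read as forecasts.

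A reader might infer that the trial's main conclusion is at risk. It is not: PFS here is descriptive and untested, and the primary endpoint, alpha, power and N=35 do not depend on it. The change is worth making before analysis because the endpoint is named, is likely to be set against other studies, and costs little to put right.

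**What to change.** - **9.6:** define PFS as the time from start of treatment to first documented progression or death from any cause, whichever comes first.
- **7.2.3:** state that patients alive without progression are censored at their last evaluable tumor assessment.
- **Hepatic PFS:** use the same form, progression in the liver or death, so that the name in 3.3 remains correct. If the separate hepatic and extra-hepatic progression-free intervals are reported without death, label them time to progression.

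Whether confirmed progression is dated at the first or the confirming scan is a separate clarification. It would also move PFS, and the sizes above do not cover it.

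The cost is wording. Dates of progression and death are already recorded (9.6, 9.7), and section 4.3.2 provides that "All subjects will be followed for survival". The downside is that reported PFS may be slightly shorter and that deaths unrelated to cancer count as events. Response criteria, the primary endpoint and the sample size stay as they are.
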